Appendix 29: Main periods Instructions to investigator for handling data rights requests ...	275
Appendix 30: Substantial amendment No. 9 to the clinical study protocol CZE	277

List of abbreviations

µmol	: micromole
ADI-R	: Autism Diagnostic Interview - Revised
ADOS-2	: Autism Diagnostic Observation Schedule, second edition
AE	: Adverse Event
AEOSI	: Adverse Event Of Special Interest
ALP	: ALkaline Phosphatase
ALT	: ALanineaminoTransferase
am	: ante meridiem
ASD	: Autism Spectrum Disorders
AST	: ASpartateaminoTransferase
bid	: bis in die (twice a day)
BMI	: Body Mass Index
BP	: Blood Pressure
bpm	: beats per minute (heart rate unit)
CARS2	: Childhood Autism Rating Scale, Second Edition
CARS2-HF	: Childhood Autism Rating Scale, Second Edition – High functioning clinical tool
CARS2-QPC	: Childhood Autism Rating Scale, Second Edition – Questionnaire for parents and caregivers
CARS2-ST	: Childhood Autism Rating Scale, Second Edition – Standard Tool
CGI	: Clinical Global Impression
CGI-I	: Clinical Global Impression – Global Improvement
CGI-S	: Clinical Global Impressions Scale
CHMP	: Committee for Medicinal Products for Human Use
cm	: Centimetre
CMP	: Clinical Monitoring Plan
CRF	: Case Report Form
CRO	: Contract Research Organisation
C-SSRS-C	: Columbia Suicide Severity Rating Scale Children’s Version
CV	: Curriculum Vitae
DBP	: Diastolic Blood Pressure
DMC	: Data Monitoring Committee
DSM-5	: Diagnostic and Statistical Manual of Mental Disorders – Fifth Edition – Text revision
DMC	: Data Safety Monitoring Board
e.g.	: Exempli gratia (for example)
E2	: Estradiol
ECG	: ElectroCardioGram
e-CRF	: Electronic Case Report Form
ENT	: Ear, Nose and Throat
ERIN	: Event Requiring Immediate Notification
g	: gram
GABA	: Gamma-aminobutyric acid
gamma GT	: Gamma-Glutamyltransferase
GCP	: Good Clinical Practice

GI	: GastroIntestinal
h	: hour
HAV	: Hepatitis A Virus
HBs	: Surface antigen of Hepatitis B virus
HBV	: Hepatitis B Virus
HCV	: Hepatitis C Virus
HDL	: High-Density Lipoprotein
HIV	: Human Immunodeficiency Virus
HR	: Heart Rate
HRT	: Hormone Replacement Therapy
i.e.	: id est (that is)
I.R.I.S.	: Institut de Recherches Internationales Servier
ICH	: International Conference on Harmonisation
ICPM	: International Classification of Procedures in Medicine
ICTR	: International Centre for Therapeutic Research
IEC	: Independent Ethics Committee
IMP	: Investigational Medicinal Product: a pharmaceutical form of an active ingredient or placebo being tested or used as a reference in a clinical trial (test drug / placebo)
IQ	: Intellectual Coefficient
IRB	: Institutional Review Board
IRS	: Interactive Response System
IU	: International Unit
IUD	: IntraUterine (contraceptive) Device
IV	: IntraVenous (route)
IVRS	: Interactive Voice Response System
IWRS	: Interactive Web Response System
K	: Kalium
kg	: kilogram
L	: Litre
LDL	: Low-Density Lipoprotein
MCV	: Mean Corpuscular Volume
MedDRA	: Medical Dictionary for Regulatory Activities
mg	: milligram
min	: minute
mL	: Millilitre
mm	: Millimetre
mmHG	: Millimetre of mercury
MMRM	: Mixed Model for Repeated Measurement
NA	: Not Applicable
Na	: Natrium
ng	: nanogram
NKCC1	: Na ⁺ /K ⁺ /2Cl ⁻ cotransporter
NS	: Not statistically Significant
OCD	: Obsessive Compulsive Disorder
PAERS	: Paediatric Adverse Event Rating Scale
PD	: Pharmacodynamics
PED QL	: Paediatric Quality of Life Inventory
PIP	: Paediatric Investigation Plan
PK	: Pharmacokinetics

pm	: post meridiem
po	: per os (orally)
PT	: Prothrombin Time
QC	: Quality Control
QTc	: QT interval corrected for heart rate
SAE	: Serious Adverse Event
SBP	: Systolic Blood Pressure
SD	: Standard Deviation
SE	: Standard Error
sec	: second
SmPC	: Summary of Product Characteristics
SRS2	: Social Responsiveness Scale, Second Edition
SSRI	: Selective serotonin reuptake inhibitor
SUSAR	: Suspected Unexpected Serious Adverse Reaction
test drug	: Drug substance in a given dosage form, tested in a clinical trial (S95008)
V	: Visit
VABS II	: Vineland Adaptive Behaviour Scales, Second Edition
WHO	: World Health Organization
WHO-DD	: World Health Organization, Drug Dictionary
yo	: Years old

1. ADMINISTRATIVE STRUCTURE OF THE STUDY

Non sponsors parties, sponsors parties and CRO responsible for local management of the study are described in a separate document entitled Administrative part of clinical study protocol.

The list of investigators for each country is given in separate documents attached to the protocol and entitled "List of investigators for [name of the country]".

The composition and role of the Data Monitoring Committee are described in sections 8.10 and 12.4.

2. BACKGROUND INFORMATION

Autism Spectrum Disorders (ASD) is a group of complex neurodevelopmental disorders characterized by the presence of multiple and persistent deficits in social communication and social interaction associated with restricted interests and stereotyped and repetitive behaviours. Aetiology of ASD is still poorly understood, but the disease appears highly genetically heritable with identified genetic mutations – despite not fully penetrant - in about 15% of the cases. Nonspecific environmental risks factors, as parental age, foetal exposure to alcohol or valproate and premature birth/ low birth weight, have also been identified.

The most frequent comorbidities and associated symptoms are: learning disabilities, sleep disturbances, epilepsies, anxiety, depression, attention problem, hyperacusis, irritability (including symptoms of aggression toward others, deliberate self-injuriousness, temper tantrums, and quickly changing moods), conduct disorder, and Obsessive Compulsive Disorder (OCD). The presence and the severity of these symptoms are very heterogeneous among patients and depend on their age.

Usual cares include global care, often in specialized institutions, and psychosocial interventions as educational measures, patients and families support and/or specific psychotherapies (mainly behavioural therapies). Associated symptoms frequently lead to drug prescription, however only second-generation antipsychotics have demonstrated clinical efficacy in behavioural disorders. Frequently prescribed off-label drugs include methylphenidate and atomoxetine for attention disorders, melatonin for sleep disorders, and selective serotonin reuptake inhibitors (SSRIs) for anxio-depressive disorders, however there is presently no approved treatment targeting core symptoms of autism.

Recent studies (Cellot, 2014) (Coghlan, 2012) suggest that GABAergic neurons and circuits may be altered in ASD. The conversion of GABA-mediated neuronal excitation into inhibition during maturation of specific neuronal populations has been reported to be altered in neurodevelopmental diseases such as autism. This lack of “GABA switch” is due to persistent high level of expression of Na⁺/K⁺/2Cl⁻ co-transporter (NKCC1) vs K-Cl co-transporters (KCC2). This in turn may lead to abnormal cell migration and differentiation, immature and imbalanced neuronal network development and thus to clinically diagnosed deficits observed in this pathology.

Levels of intracellular chloride determine the levels of neuronal inhibition and have been shown to be elevated in immature neurons and being progressively reduced within neuronal development. These observations suggest that drugs reducing intracellular chloride levels may

be helpful in normalising chloride levels and thereby restore inhibitory GABAergic function and neuronal network maturation.

Bumetanide (Burinex®) is a sulfonamide-derived loop diuretic used for the management in adult patients of oedema associated with congestive heart failure, hepatic cirrhosis and renal disease including nephropatic syndrome.

Acting centrally as a NKCC1 inhibitor, bumetanide provokes reduction of intracellular chloride, switching the aberrant excitatory action of GABA into an inhibitory action.

Up to now, the efficacy and safety of bumetanide in ASD children and adolescents have been studied in a clinical development programme consisting of 5 clinical studies (Please refer to Clinical Investigator's Brochure latest version, on section 5 for further details).

The first use of Bumetanide in ASD was a pilot study conducted in 5 children with ASD age 3 to 11 years of age (Lemonnier, 2010). This study was followed by a placebo controlled randomized phase II study in 54 ASD children (BUMEA study [NCT01078714];(Lemonnier, 2012). Of note as well, an fMRI study (academic study), carried out in open label conditions in 7 young autistic patients showed an improvement of facial processing after 1 month of bumetanide treatment (Lemonnier, 2012; Hadjikhani, 2015).

In parallel, Neurochlore sponsored a retrospective, observational study evaluating the long-term safety of Bumetanide in children and adolescents with Autism Spectrum Disorders (ASD) treated with Bumetanide on an off-label basis in the CHRU of Brest (France).

In June 2012 Neurochlore submitted a Paediatric Investigation Plan (PIP) for the condition 'Autistic Spectrum Disorder' under Article 30 of the Paediatric Regulation. It was agreed by EMA on 30 April 2013 (EMA-001303-PIP01-12).

Neurochlore carried out the phase IIb dose ranging study assessing the efficacy and safety of Bumetanide 0.5, 1.0 and 2.0mg BID doses (oral liquid formulation) in male and female patients aged ≥ 2 to ≤ 18 years of age diagnosed with ASD according to DSM-IV-TR. The main objective of the study was to determine the optimal dose of bumetanide for the pivotal phase III study. The primary criterion was the CARS scale. Three bumetanide oral solution doses, 0.5-1-2mg administered twice a day, were tested over a 3 month-treatment period. Eighty eight patients were included in the study. Using a general linear model including baseline CARS value as covariate, the difference between bumetanide 0.5 mg BID and placebo was statistically significant in the FAS -3.06 (95% CI $=[-5.63 ; -0.49]$, $p = 0.015$). When the CARS score was evaluated for 73 out of 88 patients who had a CARS value at D90 (CARS completers analysis), the results were confirmed using the general linear model for the comparison between Bumetanide 0.5 mg BID and placebo with an estimated difference at -2.93 (95% CI $=[-5.57;-0.29]$, $p= 0.026$). Bumetanide also produced significant improvements over placebo on the secondary efficacy endpoints (SRS scale, CGI-scale). On a qualitative point of view, clinicians describe that children with bumetanide are more present, more open to the world, more attentive, more participative, more willing to exchange, less hyperactive, less aggressive, less agitated and less stereotyped. The children also look more at their interlocutor. The safety profile of Bumetanide was dose-related. The best tolerability profile was observed with the Bumetanide 0.5 mg twice a day, whereas an important number of adverse events and study withdrawals were observed with Bumetanide 1.0 and 2.0 mg twice a day. Considering the 0.5mg dose is effective and presented a better safety profile than 1mg and 2mg: this dose was retained for the phase III.

Taking into account these elements, bumetanide was proposed as the first candidate allowing treatment of ASD core symptoms in paediatric population.

On the 24th February 2017, Neurochlore and Les Laboratoires Servier' entered into an agreement for development and commercialisation of the bumetanide paediatric formulation in Europe. 'Les Laboratoires Servier' takes over the phase III development program.

Following the completion of the phase II, a Committee for Medicinal Products for Human Use (CHMP) Scientific Advice procedure was performed beginning 2017 to discuss the bumetanide phase III development plan in ASD paediatric patients. A randomised, placebo controlled study design with a 6-month double-blind treatment period followed by a 6-month open labelled extension period was considered by the CHMP as the most appropriate to have a comprehensive bumetanide efficacy and safety assessment. A modification to the agreed PIP has been submitted to the Paediatric Committee (PDCO) of the European Medicine Agency (EMA) and has received a positive decision (European Medicines Agency decision EMA-001303-PIP01-12-M02 dated 10th November 2017).

The present study (CL3-95008-002) will be performed in children from 2 to less than 7 years old presenting with ASD. A 6-month double-blind treatment period will be performed in which efficacy and safety of bumetanide 0.5mg BID will be assessed *versus* placebo. This double-blind period will be followed by a 6-month open label treatment period of bumetanide 0.5mg BID in which long term safety will be evaluated and a 6 weeks discontinuation phase. Bumetanide dose will be adapted on body-weight.

The present phase III bumetanide paediatric study has been developed based on the European Guideline and validated by the Paediatric Committee in the European Medicinal Agency (European Medicines Agency decision, EMA-001303-PIP01-12-M02 dated 10th November 2017). In this development program all children (even the placebo patients) will have at least 6 months active treatment by bumetanide.

The main burden of this study for the patient is related to the outpatient centre visits to follow up the safety of the diuretic effects, which requires physical examination [including blood pressure (SBP, DBP), heart rate, body weight, height], blood and urine tests, ECG and renal ultrasound, which are of low and known risks, as well as adverse event collection. Additional burden corresponds to cognitive test evaluations which are necessary for bumetanide efficacy assessment.

The Sponsor notes that these clinical studies will be carried out in a vulnerable population and has implemented several measures in order to minimize any potential burden:

- In the framework of this Paediatric Investigational Plan endorsed by the EMA, Servier has chosen the use of scales and questionnaires to be completed as much as possible by the parents/legal representative/caregiver instead of participants. This will significantly reduce the length of a visit where the presence of the child is compulsory.
- Based on the family environment and for organizational reasons, safety evaluations required for the most time consuming visits (Selection, inclusion, visit Week 12, visit Week 26, visit Week 38 and Visit 52) could be splitted in several days.
- Regarding the management of blood sampling, all the centres selected for this study are very familiar with working with children with Autism Spectrum Disorder (ASD) and their families. In the previous studies with bumetanide in ASD paediatric population, blood samplings were found quite easily manageable by experienced

teams, and field returns reported that only the very first samplings were challenging, further ones becoming rituals. For these new studies, all efforts will be made to make the blood samplings as stress-free as possible, coordinated with daily activities as far as possible and the experience of previous trials centres will be shared with the new ones. The investigator and/or centre staff will discuss with the parents/caregivers which strategies are most likely to be successful taking into account positive or negative past experiences of participants with doctors or blood sample taking. The site will always refer to parents/Legal Representative (LR)/caregiver for behavior management, communication and child's preferences. The study team will aim to have the same experienced staff involved for each visit. The study nurse and investigator will explain what will happen before starting the venepuncture and will check the understanding when applicable. It's up to the clinical team to decide how much time is necessary to explain, distract or comfort the patient. The investigator can refer to tools used in normal practice or available at its site such as visual supports or social story boards to prepare a child for having a blood sample, with the parent/LR/caregiver support. Local anaesthesia creams or vapo-coolant spray can be used to minimise discomfort. Then, the blood samplings should be performed quickly and efficiently to avoid escalation of potential anxiety or irritability.

- All those measures contribute to the installation of a ritual much appreciated by patients with ASD.
- Sponsor highly recommends that the same person in charge of study evaluations follows a given child during the study in order to minimize any potential bias in study assessments and to reduce the burden linked to the potential stress suffered by the child.
- Paediatric liquid formulation has been specially developed for this paediatric clinical program. This formulation showed a good acceptability and palatability profile in the phase II.

For the benefit of the study, bumetanide could be the first pharmacological candidate allowing the treatment of ASD core symptoms in paediatric population, acting on a key component of the disease pathophysiology (alteration of GABAergic neurons and circuits, the conversion of GABA-mediated neuronal excitation into inhibition during maturation of specific neuronal populations being reported to be altered in neurodevelopmental diseases such as autism).

Acting centrally as a NKCC1 inhibitor, bumetanide provokes reduction of intracellular chloride, switching the aberrant excitatory action of GABA into an inhibitory action, and therefore may restore important developmental capacities.

Consequently, as there is no drug treatment for core symptoms of ASD, we set up a study with bumetanide in young developing patients with ASD in order to reduce the ASD core symptoms and functional impairment and to improve quality of life. Studies are needed in paediatric population, childhood being a time when brain plasticity is at the greatest and where behavioural and educative interventions could have the most benefit.

For the risk for the patient, the safety profile of bumetanide is similar to that reported for other loop diuretics. The target organ is the kidney and the safety profile is related to the potent diuretic activity of the compound. Based on the safety experience gained at this stage of drug development in ASD (5 clinical studies described above), the safety profile of bumetanide in ASD children and adolescents seems comparable to the one observed in adult patients treated for oedema. Despite the penetration of bumetanide into brain, no toxic effects on the Central Nervous System have been observed.

The emergent bumetanide safety profile observed in paediatric population with ASD was mainly related to bumetanide diuretic effect (enuresis, pollakiuria, polyuria, electrolyte disturbances and dehydration) and was dose-related. It did not differ from that of bumetanide tablets. Hypokalaemia is an identified risk and therefore blood potassium level will be regularly monitored during the phase III bumetanide paediatric program (blood potassium sampling schedule validated with the EMA). It has to be highlighted that all hypokalaemia reported during the phase II NeuroClin02 dose-range study were asymptomatic (and without any cardiac impact), and thus it is crucial to perform all planned samplings. Lastly, the most favourable tolerability profile was observed with bumetanide 0.5 mg twice a day corresponding to the dose that will be given during the 2 phase III studies.

Considering the targeted population of patients, a Data Monitoring Committee (DMC) will be set up and will be responsible for periodic review of patient's safety data throughout the study. Details on the role and organisation of the DMC will be provided in a separate charter. The study will be carried out in compliance with the protocol, GCP, the ethical principles that have their origin in the Declaration of Helsinki and the applicable regulatory requirements.

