8.6. Definition of Adverse event of special interest

An adverse event of special interest (AEOSI) is one of scientific and medical interest or concern regarding the IMP for which recording rules, special documentation such as hospital records and/or adjudication committee could be appropriate. It may be a serious or non-serious AE that may require further investigation in order to characterize and understand.

In the framework of this study protocol AEOSI include any biological Potassium electrolyte abnormality < 3.5 mEq/L.

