10.2.2.6. Safety analysis

10.2.2.6.1. Adverse events

Double-blind treatment period:

Number of events, number and percentage of patients reporting at least one event, presented by primary system organ class, and preferred term will be provided for serious adverse events and emergent adverse events under treatment during the double-blind treatment period in the Safety Set.

Emergent adverse events will be described according to the seriousness, the intensity, the relationship, the action taken regarding the IMP, the requirement of added therapy, and the outcome.

Of note, the seriousness and the relationship to the IMP of the adverse event correspond to the investigator opinion or, in case of events upgraded by the sponsor for seriousness or for causality in case of SAE, to the sponsor opinion.

Open-label active treatment period:

The same analysis will be performed for adverse events occurred or worsened during the open-label active treatment period in the Safety Set.

Post-treatment period:

All adverse events reported after the last study drug intake will be listed.

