3.6. Safety analysis

All safety analyses will be performed on the taken treatment at W000 as following:

- For the double-blind period in the SS by treatment group (S95008 vs placebo).
- For the open-label period: in the SSO on the Placebo/S95008 arm.
- For the combined period: in the SSC on the S95008/S95008 arm.

Six periods are of interest to present accurately the safety endpoints. The start and end date of these periods are summarized in the following table:

Table (3.6) 1 - Definition of periods of emergence for safety events

| Period ID | ANALYSIS PERIOD | START | END |
|------------------|--|--|--|
| #1 | Emergent during the double-blind period | First intake in double-blind | End of double-blind period (including W26) |
| #2 | Treatment Emergent during the double-blind period | First intake in double-blind | Min(Last intake in double-blind + 2 days, First intake in open-label) |
| #3 | Emergent during the open-label period | First intake in open-label (W26 not included) | End of open-label period (including W52 and follow-up) |
| #4 | Treatment Emergent during the open-label period | First intake in open-label (W26 not included) | Last intake in open-label + 2 days (included) |
| #5 | Emergent from the combined period | First intake in double-blind | End of open-label period (including W52 and follow-up) |
| #6 | Treatment Emergent from the combined period | First intake in double-blind | Last intake in open-label + 2 days (included) |

Listing of main safety data (including adverse events) and start/end date of each period will be provided for:

- Patients who had a delay superior to 30 days between the double-blind and the open-label period will be listed separately.

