3.6.1. Adverse events

Definition:

- **Emergent Adverse Events (EAE)** during the double-blind (*resp. open-label, combined*) period are defined as all adverse events which occur in the period #1 (*resp. #3, #5*) (as per table above), or which started strictly before period #1 (*resp. #3, #5*) but which worsen (in terms of intensity) or become serious according to the investigator opinion during period #1 (*resp. #3, #5*).
- **Treatment Emergent Adverse Events (TEAE)** during the double-blind (*resp. open-label, combined*) period are defined as all adverse events which occur in the period #2 (*resp. #4, #6*) (as per table above), or which started strictly before period #2 (*resp. #4, #6*) but which worsen (in terms of intensity) or become serious according to the investigator opinion during period #2 (*resp. #4, #6*).
- **AE starting during the run-in period** are defined as all adverse events which started strictly before period #1.

Analyses:

Number of events as well as number, percentage and annual incidence rate of patients reporting at least one event, presented by primary System Organ Class (SOC), and Preferred Term (PT), will be provided for:

- Serious EAE and deaths for period #1, #3 and #5.
- TEAE, TEAE leading to IMP withdrawal, TEAE requiring new treatment or increase of ongoing treatment, TEAE requiring surgical or medical procedure, TEAE related to IMP, serious TEAE, severe TEAE, non-serious TEAE for periods #2, #4 and #6.

TEAE will be described according to the seriousness, the intensity, the relationship with the IMP, the action taken regarding the IMP, the requirement of added therapy and the outcome.

Moreover, TEAE, TEAE related to IMP and serious TEAE will be presented according to their time to onset in weeks calculated from the start of the period #2 (*resp. #4 and #6*).

AE starting during the run-in period will be also described by SOC and PT in the SS.

All adverse events reported after the last Bumetanide intake + 2 days (excluded) will be listed. All COVID-19 infection reported during the study will be listed.

Number of events as well as number, percentage of patients reporting at least one event, presented by primary System Organ Class (SOC), and Preferred Term (PT), will be provided for all AE and all serious AE occurring after the first intake in the extension part in the patients included in the extension period.

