3.6.3. Clinical laboratory evaluation

Definition:

- A laboratory value is considered as analysable if non-missing and not flagged in the ClinTrial database as "not analysable".
- The analyses will be performed on periods #2, #4 and #6.
- A value is considered as occurring during the considered period if the sampling date is between the start and last date of the considered period.
- Baseline for each period is defined in Section 3.1.2.
- For each considered period:
 - High emergent abnormal value under treatment according to the laboratory reference ranges is defined as value \leq ULN (Upper Limit of Normal laboratory reference range) or missing at the baseline of the considered period and $>$ ULN under treatment.
 - Low emergent abnormal value under treatment according to the laboratory reference ranges is defined as value \geq LLN (Lower Limit of Normal laboratory reference range) or missing at baseline of the considered period and $<$ LLN under treatment.

- High emergent abnormal value under treatment according to the cut-offs for PCSA values is defined as value \leq ULS (Upper Limit used to define potentially clinically Significant abnormal values) or missing at baseline of the considered period and $>$ ULS under treatment.
- Low emergent abnormal value under treatment according to the cut-offs for PCSA values is defined as value \geq LLS (Lower Limit used to define potentially clinically Significant abnormal values) or missing at baseline of the considered period and $<$ LLS under treatment.

Analyses:

For each biochemical, haematological (blood and urine sample) parameter and for electrolytes monitoring (Potassium, Sodium), the following analysis will be performed for each period:

- Number and percentage of patients with at least one high/low emergent abnormal value under treatment, according to the laboratory reference ranges and to the cut-offs for PCSA values.
- Laboratory parameters classified (number and percentage of patients in each class) according to these reference ranges and cut-offs and using shift tables from baseline in the considered period to the worst (high and/or low) values under treatment.

Moreover, listings of patients with out-of-range or PCSA analysable values emergent under treatment in each period and of non-analysable values excluded from analyses will be provided.

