Additionally, for potassium parameter, number and percentage of patients with hypokalaemia will be described by severity (mild: $3\text{mEq/L} \leq K^+ < 3.5 \text{ mEq/L}$ / moderate: $2.2\text{mEq/L} \leq K^+ < 3 \text{ mEq/L}$ / severe: $K^+ < 2.2\text{mEq/L}$) in each period.

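### The expected diuretic harm is spread over several event terms, and no table specified in the protocol or SAP counts the children with at least one such adverse event

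*Protocol*

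**What the plan says.** Protocol section 2 (Background information) describes the emergent profile in the paediatric ASD population as "mainly related to bumetanide diuretic effect (enuresis, pollakiuria, polyuria, electrolyte disturbances and dehydration) and was dose-related". The sponsor thus places five kinds of event under one mechanism. Assessing safety is a secondary objective (Protocol 3.2).

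SAP 3.6.1 gives event counts, and patient counts with percentages and annual rates, "presented by primary System Organ Class (SOC), and Preferred Term (PT), will be provided for" serious emergent events and deaths, all treatment-emergent adverse events (TEAEs), and TEAE subsets such as related, serious, severe or leading to withdrawal of study drug. It adds that "TEAE will be described according to the seriousness, the intensity, the relationship with the IMP", the action taken, added therapy and outcome, and it presents time to onset. Protocol 10.2.2.6.1 uses the same layout: "presented by primary system organ class, and preferred term will be provided for serious adverse events and emergent adverse events under treatment".

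The laboratory section goes part of the way. In SAP 3.6.3, emergent abnormal values and shift tables are planned for blood and urine parameters "and for electrolytes monitoring (Potassium, Sodium), the following analysis will be performed for each period", and "for potassium parameter, number and percentage of patients with hypokalaemia will be described by severity". Protocol 8.6 states that "AEOSI include any biological Potassium electrolyte abnormality < 3.5 mEq/L".

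Under SAP 3.6, the double-blind period is reported by treatment group in the Safety Set. The open-label period covers only the placebo/bumetanide arm, and the combined period only the bumetanide/bumetanide arm.

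**The concern.** The main expected harm is known in advance, yet the planned adverse event tables divide it by coding term. A child reported with enuresis and a child reported with pollakiuria enter different PT rows, although the protocol treats both as the same drug effect. A reader of the planned tables could not state how many children per arm had that effect.

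Two things are at stake. With about 100 children per arm, several small differences each look compatible with chance when the combined difference might not. And if the grouping is done only after unblinding, the choice of terms can be criticised as driven by the data.

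**Working it through.** **The plan's own figure.** Neither document gives a rate for diuretic-effect events. The only design figure that can be reproduced is the sample size (Protocol 10.1, SAP 1.3), which fixes the arm size used below. For a standardised effect of 0.5, two-sided 0.05 and 90% power, n per arm = 2 × (1.960 + 1.282)² / 0.5² = 84.1, so 85 per arm and 170 in total. Allowing for 15% withdrawal, 170 / 0.85 = 200, or about 100 per arm. Both figures reproduce.

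**Which planned outputs could supply the count?**

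| Output | What it gives | What it leaves out |
|---|---|---|
| PT rows (SAP 3.6.1) | children with each single term | children with any of the terms |
| SOC rows (SAP 3.6.1) | each child once per SOC | unrelated events are mixed in; the documents do not say which SOC holds each term |
| Related TEAEs (SAP 3.6.1) | events judged related to study drug | again split by SOC and PT; any total mixes mechanisms |
| Potassium classes (SAP 3.6.3) | 3 to <3.5, 2.2 to <3 and <2.2 mEq/L, which together are all values <3.5 | enuresis, pollakiuria, polyuria, dehydration |
| Potassium and sodium abnormalities (SAP 3.6.3) | emergent high and low values | the same four kinds of event |

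None gives children with at least one diuretic-effect adverse event.

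**Can the count be rebuilt from PT rows?** If the PT counts in an arm of N children are n1, …, nk, the number with any event lies between max(ni) and min(N, n1 + … + nk).

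- Five PTs at 10 of 100 each: between 10 and 50 children.
- Three PTs at 8 of 100 each: between 8 and 24. At 3 of 100 each: between 3 and 9. PT rows of 8 versus 3 therefore allow a grouped difference anywhere from 8 - 9 = -1 to 24 - 3 = +21 points.

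**Size, under assumed rates.** Take 100 per arm and the three urinary terms named in the protocol (enuresis, pollakiuria, polyuria). The interval is d ± 1.96 × √[p1(1-p1)/100 + p0(1-p0)/100]. Under independence the grouped risk is 1 - (1-p)³.

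*8% versus 3% per term*
- Single PT row: d = 5.0; SE = √(0.000736 + 0.000291) = 0.0320; 95% CI -1.3 to 11.3.
- Grouped, independent: 1 - 0.92³ = 22.1% versus 1 - 0.97³ = 8.7%; d = 13.4; SE = √(0.001723 + 0.000797) = 0.0502; 95% CI 3.6 to 23.2.
- Grouped, full overlap: 8% versus 3%, identical to one PT row.

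*6% versus 2% per term*
- Single PT row: d = 4.0; SE = √(0.000564 + 0.000196) = 0.0276; 95% CI -1.4 to 9.4.
- Grouped, independent: 1 - 0.94³ = 16.9% versus 1 - 0.98³ = 5.9%; d = 11.1; SE = √(0.001407 + 0.000554) = 0.0443; 95% CI 2.4 to 19.7.
- Grouped, full overlap: 6% versus 2%, identical to one PT row.

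**The case against.** The strongest reply is that much of this is already covered and the rest is a matter of presentation. Several parts of it stand.

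- **Hypokalaemia.** A reader might infer that the adverse event of special interest goes unreported because SAP 3.6.1 has no table under that name. The documents do not support this. The event is defined by a potassium value, and the three severity classes in SAP 3.6.3 together cover every value below 3.5 mEq/L, by arm in the double-blind period. No further table is needed for it.
- **SOC rows.** A reader might infer that the urinary terms are never pooled. A SOC row counts each child once and will pool those terms that share a SOC. It also takes in unrelated events, and the documents do not give the hierarchy, so it is not a count of the diuretic effect.
- **Overlap.** Events from one mechanism tend to occur in the same children, so independence is generous, and with full overlap grouping gains no precision. That is correct. The grouped row would then show that the effect is confined to a few children, which PT rows cannot show.
- **Descriptive safety.** No safety test is planned, and SAP 3.4.1 excludes p-values outside the primary analysis. The comparison of intervals above measures visibility only; no decision rule is affected.
- **Retained data.** Patient-level coded events allow a grouped count later. What is lost is pre-specification of the list, not the information.

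What the reply does not remove is that the urinary and dehydration events have no combined count in either document.

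**Conclusion.** The point holds in a limited form. The protocol names a mainly diuretic, dose-related effect as the expected harm. No table specified in the protocol or SAP gives the number of children with at least one such adverse event, and PT rows cannot be summed to obtain it. The gap lies chiefly in the urinary and dehydration terms; the electrolyte part is largely covered by laboratory data.

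At the assumed 8% versus 3% per urinary term, the grouped difference would be +13.4 points under independence and +5.0 under full overlap, against +5.0 in each PT row. These rates, and the overlap being the same in both arms, are assumptions.

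Two wider readings are not supported. The protocol says the profile was mainly diuretic, so not all emergent harm belongs in the group. And SAP section 1 places the table templates in a separate document that is not available here, so it cannot be said that no such table exists. A grouped term and its PT list are nevertheless analysis definitions and belong in the SAP.

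**What to change.** In SAP 3.6.1, define a diuretic-effect group by a PT list fixed before unblinding, at the blind review described in Protocol 14.2. Add to the TEAE output:

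- a sub-row for urinary terms (enuresis, pollakiuria, polyuria and related micturition terms);
- a sub-row for dehydration and volume depletion;
- an overall row for children with at least one diuretic-effect TEAE, with a statement of whether electrolyte abnormalities found only in laboratory data count.

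Give the number of children, the percentage and the annual incidence rate. For period #2 (treatment-emergent, double-blind), report by arm with the between-arm difference and its 95% CI, without a p-value. For periods #4 and #6, which each have one arm, report descriptively.

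The cost is SAP wording, a brief medical decision on the PT list, and one extra table per period. Treatment, visits and data collection do not change.
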